7.1.4.3 Maintenance phase

Patients who continue to achieve CR/CRI after (up to) four cycles of consolidation therapy will receive midostaurin maintenance therapy. Prior to initiation of midostaurin maintenance

therapy, all significant acute toxicity from consolidation therapy must have resolved to < grade 2.

For CR patients, midostaurin maintenance therapy will begin after hematologic recovery (ANC \geq 1 000/ μ L, platelet count \geq 100 000/ μ L) occurs and for CRi patients per investigator discretion and at least 3 days and no later than 28 calendar days after the last dose of consolidation midostaurin.

Each maintenance cycle is 28 days treatment. Subsequent cycles start on the day after the previous cycle is completed. In other words, subsequent cycles start 29 calendar days from the start of the previous cycle.

Patients who are unable to complete the cytarabine consolidation cycles because of toxicity or insufficient hematologic recovery may still be eligible for maintenance therapy. Discuss this situation in advance with the Novartis Study Team.

Refer to [Table 6-3](#) for maintenance treatment schedule.

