7.1.4.2 Consolidation phase

Patients who achieved a CR/CRI after either one or two induction cycles will receive consolidation therapy with cytarabine as defined by NCCN treatment guidelines plus subsequent midostaurin during each cycle. Patients will receive up to four cycles of consolidation therapy. Fewer cycles are accepted as per investigator’s discretion.

Each consolidation cycle is 28 days treatment. It is recommended that subsequent cycle start at least 3 days after the previous cycle is completed and no later than 70 calendar days from the start of the first cycle of consolidation. For the other consolidation cycles a recovery periods of 21 days maximum will be applied. Refer to [Table 6-2](#) for consolidation treatment schedule.

An end phase disposition will be completed prior the C1D1 of the maintenance phase.

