7.2 Assessment types

7.2.1 Efficacy assessments

Induction therapy

FLT3 mutated patients will receive induction therapy (cytarabine with anthracycline (idarubicin or daunorubicin) (for details refer to [Section 6.1.1](#)) sequentially followed by midostaurin.

In the first Induction phase, a bone marrow aspiration will be performed in all patients on Day 21-28 (according to local standard of care) to determine the need for a second induction cycle. If the marrow aspirate is inadequate to make a determination, repeat the bone marrow assessment within one week.

If the Day 21-28 (according to local standard of care) bone marrow aspiration reveals <5% blasts in a cellular marrow (> 20%), then a bone marrow aspiration must be performed within one week after recovery of ANC $\geq 1\,000/\mu\text{L}$ and platelets $\geq 100\,000/\mu\text{L}$ to document complete remission. Patients in CR will proceed to consolidation therapy. Patients with CRI will proceed to consolidation therapy as per investigator discretion.

If the Day 21-28(according to local standard of care) bone marrow aspiration reveals $\geq 5\%$ leukemic blasts in a cellular marrow (> 20%) a second induction will be given.

Second Induction therapy (if applicable)

For patients requiring a second induction, treatment will begin at least 3 days after completing midostaurin.

Bone marrow aspiration will be performed within one week after recovery of ANC $\geq 1000/\mu\text{L}$ and platelets $\geq 100,000/\mu\text{L}$ to assess for response.

Patients in CR will proceed to consolidation therapy. Patients who have residual AML at this time after a second remission induction should be removed from protocol therapy. Patients with CRI will proceed to consolidation therapy as per investigator's discretion.

Consolidation therapy (up to four cycles per investigator's discretion)

Based upon the superior results reported for AML patients less than 60 years old with normal karyotypes in prospective clinical trials ([Farag et al 2005](#)) and RATIFY, who achieve a CR/CRI after induction will receive further therapy with midostaurin. Patients will receive up to four cycles of consolidation therapy. Each consolidation cycle is four weeks in duration, and should begin within two weeks following hematologic recovery (ANC $\geq 1000/\mu\text{L}$, platelet count $\geq 100,000/\mu\text{L}$), but not sooner than 31 days from the beginning of the previous cycle. If a

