remission consolidation cycle is delayed > 8 weeks (56 days) from the start of the previous course due to slow resolution of toxicity or slow recovery of complete blood counts (CBC), please contact Novartis. A bone marrow aspiration must be performed prior to the first consolidation cycle C1D1 and later can be performed if necessary per investigator's decision at any time during consolidation phase.

Maintenance therapy (for patients in CR/CRi after consolidation therapy)

Patients who continue in CR/CRi (by bone marrow aspiration and blood evaluation) after four cycles of remission consolidation therapy will receive midostaurin. Prior to maintenance therapy, all significant acute toxicity from consolidation therapy must have resolved to \leq grade 2.

Patients with CRi will proceed to maintenance therapy as per investigator's discretion and for CR patients maintenance therapy will begin after hematologic recovery (ANC \geq 1000/ μ L, platelet count \geq 100,000/ μ L) from remission consolidation, and at least 3 days after the last dose of midostaurin during consolidation. Patients who are unable to complete four courses of HiDAC consolidation because of toxicity may still be eligible for maintenance therapy at the discretion of the principal investigator after the last dose of consolidation after recovery from hematologic and other significant acute toxicity. A bone marrow examination should be performed prior to the first maintenance and every 3 months during maintenance phase.

Based on the results of this bone marrow examination (during maintenance phase) the physician will decide if the patient pursues the study treatment.

- Complete remission (CR): Bone marrow blasts <5% with spicules; absence of blasts with Auer rods; absence of extramedullary disease; absolute neutrophil count (ANC) \geq 1000/ μ L; platelet count \geq 100,000/ μ L; independent of transfusions.
Transfusion independence is defined as at least 7 days transfusion free prior to CR/CRi assessments.
- CR with incomplete recovery (CRi): All CR criteria except for residual neutropenia ($<1000/\mu$ L) or thrombocytopenia ($<100,000/\mu$ L) with transfusion independence but persistent cytopenia.
- Partial remission (PR) is designated by normalization of blood values but with a decrease from baseline of at least 50% in the percentage of blasts to 5% to 25% in the bone marrow aspirate. A value of \leq 5% blasts may also be considered a PR if Auer rods are present.

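### Protocol 7.1.4.3 and 7.2.1 both set entry rules for maintenance and disagree, chiefly on patients who stopped consolidation early with low counts and on residual grade 2 toxicity

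*Protocol*

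**What the plan says.** Two protocol sections tell sites who may start maintenance.

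Section 7.1.4.3 gives the general rule: "Patients who continue to achieve CR/CRI after (up to) four cycles of consolidation therapy will receive midostaurin maintenance therapy". For patients who stop consolidation early it adds: "Patients who are unable to complete the cytarabine consolidation cycles because of toxicity or insufficient hematologic recovery may still be eligible for maintenance therapy", followed by "Discuss this situation in advance with the Novartis Study Team". Significant acute toxicity must first have fallen below grade 2. Patients in CR wait for ANC and platelet recovery, and patients in CRi start at the investigator's discretion. The start falls between 3 and 28 calendar days after the last consolidation dose of midostaurin.

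The maintenance paragraphs of Section 7.2.1 say that patients still in CR/CRi "after four cycles of remission consolidation therapy will receive midostaurin". Early stoppers are handled thus: "Patients who are unable to complete four courses of HiDAC consolidation because of toxicity may still be eligible", and this is "at the discretion of the principal investigator after the last dose of consolidation after recovery from hematologic and other significant acute toxicity". Significant acute toxicity must have fallen to grade 2 or below. The start is at least 3 days after the last midostaurin dose, with no latest day.

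On the length of consolidation, Section 7.1.4.2 says "Fewer cycles are accepted as per" the investigator's judgement, and the consolidation paragraph of 7.2.1 itself says "Patients will receive up to four cycles of consolidation therapy". Section 7.1 leaves the number of cycles in every phase to the investigator.

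**The concern.** Both sections are written as instructions. On maintenance entry neither refers to the other, and nothing says which prevails.

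The entry rule shapes the results. Maintenance is one of the three phases in the primary safety objective and in the CR/CRi objective (Protocol Table 3-1). Each period is made up of everyone who entered it (Protocol 10.5.3.1, SAP 2.1.1), and AEs and response are reported by period (SAP 2.9.1 and 2.7.1). If sites follow different sections, the maintenance group differs by site at its margin: early stoppers, patients with low counts, patients with residual toxicity. These patients plausibly differ from the rest in safety and relapse risk.

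Deviation status is also unclear. Protocol Section 12 allows no authorized deviations and has significant ones reported in the CSR, and Section 7.1.5 lists a protocol deviation among the circumstances for withdrawal from treatment. An entry that is proper under one section could be classed as a deviation under the other.

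**Working it through.** The plan gives no figure to reproduce, so the check sets the two sections side by side and then runs test patients through both.

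| Condition | 7.1.4.3 | 7.2.1 | Result |
|---|---|---|---|
| Reason for stopping consolidation early | Toxicity, or counts that did not recover enough | Toxicity only | Differ |
| Recovery asked of early stoppers | None beyond the general CR and CRi rules | Recovery from hematologic and other acute toxicity | Differ, for CRi only |
| Residual acute toxicity | Below grade 2 | Grade 2 or below | Differ at grade 2 |
| Latest start | Day 28 after last consolidation midostaurin | Not stated | Omission in 7.2.1 |
| Consolidation cycles | Up to four | Four, with an exception for toxicity | 7.2.1 out of line |
| Who is involved for early stoppers | Advance discussion with the sponsor | Principal investigator's discretion | Compatible |
| Count thresholds for CR | ANC 1000/µL, platelets 100,000/µL | Same | Agree |
| Entry in CRi | Investigator's discretion | Same | Agree |

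**Patient A.** Stopped consolidation early because counts did not recover; in CRi, counts still low. Under 7.1.4.3 the reason for stopping is listed and CRi entry is discretionary, so the patient may enter. Under the early-stopper sentence of 7.2.1 the reason is not listed and hematologic recovery is required, so the patient may not.

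**Patient B.** Meets every other condition, with a residual grade 2 acute toxicity. Not admitted by 7.1.4.3; admitted by 7.2.1.

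**Patient C.** In CR after four cycles; counts recover on day 35 after the last midostaurin dose. Since 35 − 28 = 7, the patient is 7 days past the limit in 7.1.4.3. Section 7.2.1 is silent. The sentence in 7.1.4.3 could be read as tying the 28 days to CRi patients only; a CRi patient on day 35 then stands in the same position.

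**Patient D.** In CR after two cycles by the investigator's choice, without limiting toxicity. Covered by 7.1.4.3. Not covered by the maintenance sentence of 7.2.1 taken alone, but covered once that sentence is read with 7.1, 7.1.4.2 and the consolidation paragraph of 7.2.1.

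**Patient E.** Stopped early for toxicity and has since recovered. May be eligible under both sections.

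Patients A and B get opposite answers. C shows an omission, D loose wording, and E no conflict.

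**The case against.** The best case for the plan is that most of the differences are silence or shorthand.

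- **Latest start.** A site that keeps to 28 days satisfies both sections, and nothing in 7.2.1 grants a later start. This stands: it is an omission, not a contradiction.
- **Cycles.** Section 7.2.1 itself says up to four, and 7.1.4 lets patients who keep their remission after consolidation go on without naming a minimum. This largely stands. The phrase needs correcting, but it would bar patient D only if cut off from its own section.
- **Sponsor discussion.** Discussing a case in advance is not the same as needing approval, so the investigator can discuss and then decide. This stands: it is a difference of process.
- **Counts.** In 7.1.4.3 poor count recovery is a reason for stopping cytarabine, not a waiver of recovery before maintenance; CR patients must recover under both sections. This stands, and it narrows the conflict to early stoppers in CRi. It does not remove it.

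A reader might infer that the sections clash outright on every condition, or that anyone with one to three consolidation cycles is eligible under one and barred under the other. The documents do not support that, as patients D and E show.

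It can also be said that a site could always take the narrower limit and so breach neither section. True, but the protocol does not tell sites to do so, and a site that does not is still following a written rule.

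Finally, the trial is single-arm with no hypothesis test, and the period denominator is defined by actual entry. The analysis rule is therefore clear; only the make-up of the group can vary.

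**Conclusion.** The inconsistency is real but narrow. Two conditions give opposite answers for an identifiable patient: the early stopper in CRi with persistently low counts, and the patient with residual grade 2 acute toxicity. Two more need tidying: the latest start missing from 7.2.1 and its wording on four cycles.

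The size cannot be stated. The documents do not say how many patients stopped consolidation early, were in CRi at that point, or had residual grade 2 toxicity. No test or error rate is affected. The effect is on the composition of the maintenance group and on deviation counts, and the mismatch also leaves sites with conflicting directions on a matter of patient safety.

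The conclusion rests on three assumptions:

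- For patient A, the specific early-stopper sentence in 7.2.1 prevails over that section's general discretion for CRi.
- The low counts that define CRi are not themselves caught by the general acute-toxicity condition. The discretion that both sections give for CRi implies this.
- For patient B, the two grade symbols were read correctly from the PDF. If they turn out to be the same, that conflict falls away and patient A's remains.

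**What to change.** Reconcile the two passages into one list of maintenance entry criteria, kept in one section, with a cross-reference from the other. The list should cover consolidation cycles completed, accepted reasons for stopping early, count recovery for CR, CRi and early stoppers, the residual toxicity grade, the latest start day, and who is consulted. The sponsor must decide which conditions apply; this review takes no view on which clinical rule is right. While patients can still enter maintenance, the cost is wording in an amendment and a site notice, with no new procedure. Some patients admitted under one reading may no longer qualify.

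The SAP records enrollment complete at 301 patients and a last revision after database lock, so an amendment may no longer change who entered. In that case:

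- State in the CSR which section governs the classification of deviations at maintenance entry.
- Tabulate maintenance entrants by consolidation cycles completed, reason for stopping consolidation, and days from the last consolidation midostaurin dose to the start of maintenance, labeled as a post-lock description.

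This needs no new data collection. First and last dosing dates are derived by period (SAP 2.1.1), exposure is summarized by cycle (SAP 2.5.2), and Protocol 7.1.4.2 requires an end-of-phase disposition before maintenance. The documents do not show that page's fields, so the reason for stopping can be tabulated only as far as the page records it. The cost is one table and a sentence.

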7.1.5 Discontinuation of study treatment

At the time patients discontinue study treatment; a visit should be scheduled as soon as possible, at which time all of the assessments listed for the End of Treatment visit will be performed. An End of Treatment eCRF page should be completed, giving the date and reason for stopping the study treatment.

Patients who discontinue study treatment should be considered withdrawn from the study after the final visit assessments are performed or when it is clear that the patient will not return for these assessments.

If a study withdrawal occurs, or if the patient fails to return for visits, the Investigator must determine the primary reason for a patient's premature withdrawal from the study and record this information in eCRF.

At minimum, patients who discontinue study treatment, including those who refuse to return for a final visit will be contacted for safety evaluations. All patients must have safety evaluations for 30 days, after the last dose of study treatment unless they have withdrawn consent.

Patients may voluntarily discontinue from the study treatment for any reason at any time. If a patient decides to discontinue from the study treatment, the investigator should make a reasonable effort (e.g. telephone, e-mail, letter) to understand the primary reason for this decision and record this information in the patient's chart and on the appropriate eCRF pages. They may be considered withdrawn if they state an intention to withdraw, fail to return for visits, or become lost to follow-up for any other reason.

The investigator should discontinue study treatment for a given patient if; he/she believes that continuation would be detrimental to the patient's well-being.

Patients may be withdrawn from study treatment under the following circumstances:

- Adverse events
- Pregnancy
- Subject withdrew consent

- Lost to follow up
- Technical problems
- Death
- Progressive disease*
- Protocol deviation
- Study terminated by sponsor
- Investigator decision
- Subject/guardian decision

*The progressive disease refers to CR/CRi not achieved at the end of induction and/or consolidation therapy and relapse.

7.1.5.1 Replacement policy

Not Applicable

Escalation part:

Not Applicable

Expansion part:

Not Applicable

7.1.6 Withdrawal of consent

Patients may voluntarily withdraw consent to participate in the study for any reason at any time. Withdrawal of consent occurs only when a patient does not want to participate in the study any longer, and does not want any further visits or assessments, and does not want any further study related contact.

Novartis will continue to retain and use all research results that have already been collected for the study evaluation. All biological samples that have already been collected may be retained and analyzed at a later date (or as required by local regulations).

If a patient withdraws consent, the investigator should make a reasonable effort (e.g. telephone, e-mail, letter) to understand the primary reason for this decision and record this information.

Study treatment must be discontinued and no further assessments conducted.

Further attempts to contact the patient are not allowed unless safety findings require communication or follow up.

7.1.7 Follow up for safety evaluations

All patients must have safety evaluations for 30 days, after the last dose of study treatment except if a patient withdraws consent.

Data collected should be added to the Adverse Events CRF and the Concomitant Medications CRF.

7.1.8 Lost to follow-up

For patients whose status is unclear because they fail to appear for study visits without stating an intention to withdraw consent, the investigator should contact the patient, the family or the family physician, as agreed in the informed consent and document in the source documents all the steps taken to contact the patient, e.g. dates of telephone calls, registered letters, etc. A patient should not be considered lost to follow-up until due diligence has been completed. Patients lost to follow up should be recorded as such on the appropriate Disposition CRF.

7.2 Assessment types

7.2.1 Efficacy assessments

Induction therapy

FLT3 mutated patients will receive induction therapy (cytarabine with anthracycline (idarubicin or daunorubicin) (for details refer to [Section 6.1.1](#)) sequentially followed by midostaurin.

In the first Induction phase, a bone marrow aspiration will be performed in all patients on Day 21-28 (according to local standard of care) to determine the need for a second induction cycle. If the marrow aspirate is inadequate to make a determination, repeat the bone marrow assessment within one week.

If the Day 21-28 (according to local standard of care) bone marrow aspiration reveals <5% blasts in a cellular marrow (> 20%), then a bone marrow aspiration must be performed within one week after recovery of ANC $\geq 1\,000/\mu\text{L}$ and platelets $\geq 100\,000/\mu\text{L}$ to document complete remission. Patients in CR will proceed to consolidation therapy. Patients with CRI will proceed to consolidation therapy as per investigator discretion.

If the Day 21-28(according to local standard of care) bone marrow aspiration reveals $\geq 5\%$ leukemic blasts in a cellular marrow (> 20%) a second induction will be given.

Second Induction therapy (if applicable)

For patients requiring a second induction, treatment will begin at least 3 days after completing midostaurin.

Bone marrow aspiration will be performed within one week after recovery of ANC $\geq 1000/\mu\text{L}$ and platelets $\geq 100,000/\mu\text{L}$ to assess for response.

Patients in CR will proceed to consolidation therapy. Patients who have residual AML at this time after a second remission induction should be removed from protocol therapy. Patients with CRI will proceed to consolidation therapy as per investigator's discretion.

Consolidation therapy (up to four cycles per investigator's discretion)

Based upon the superior results reported for AML patients less than 60 years old with normal karyotypes in prospective clinical trials ([Farag et al 2005](#)) and RATIFY, who achieve a CR/CRI after induction will receive further therapy with midostaurin. Patients will receive up to four cycles of consolidation therapy. Each consolidation cycle is four weeks in duration, and should begin within two weeks following hematologic recovery (ANC $\geq 1000/\mu\text{L}$, platelet count $\geq 100,000/\mu\text{L}$), but not sooner than 31 days from the beginning of the previous cycle. If a

remission consolidation cycle is delayed > 8 weeks (56 days) from the start of the previous course due to slow resolution of toxicity or slow recovery of complete blood counts (CBC), please contact Novartis. A bone marrow aspiration must be performed prior to the first consolidation cycle C1D1 and later can be performed if necessary per investigator's decision at any time during consolidation phase.

Maintenance therapy (for patients in CR/CRi after consolidation therapy)

Patients who continue in CR/CRi (by bone marrow aspiration and blood evaluation) after four cycles of remission consolidation therapy will receive midostaurin. Prior to maintenance therapy, all significant acute toxicity from consolidation therapy must have resolved to \leq grade 2.

Patients with CRi will proceed to maintenance therapy as per investigator's discretion and for CR patients maintenance therapy will begin after hematologic recovery (ANC \geq 1000/ μ L, platelet count \geq 100,000/ μ L) from remission consolidation, and at least 3 days after the last dose of midostaurin during consolidation. Patients who are unable to complete four courses of HiDAC consolidation because of toxicity may still be eligible for maintenance therapy at the discretion of the principal investigator after the last dose of consolidation after recovery from hematologic and other significant acute toxicity. A bone marrow examination should be performed prior to the first maintenance and every 3 months during maintenance phase.

Based on the results of this bone marrow examination (during maintenance phase) the physician will decide if the patient pursues the study treatment.

- Complete remission (CR): Bone marrow blasts <5% with spicules; absence of blasts with Auer rods; absence of extramedullary disease; absolute neutrophil count (ANC) \geq 1000/ μ L; platelet count \geq 100,000/ μ L; independent of transfusions.
Transfusion independence is defined as at least 7 days transfusion free prior to CR/CRi assessments.
- CR with incomplete recovery (CRi): All CR criteria except for residual neutropenia ($<1000/\mu$ L) or thrombocytopenia ($<100,000/\mu$ L) with transfusion independence but persistent cytopenia.
- Partial remission (PR) is designated by normalization of blood values but with a decrease from baseline of at least 50% in the percentage of blasts to 5% to 25% in the bone marrow aspirate. A value of \leq 5% blasts may also be considered a PR if Auer rods are present.
- Treatment failure includes patients for whom treatment that failed to achieve a CR/CRi or equal or less than a PR.
- Relapse/recurrence following complete response is a reappearance of leukemic blasts in the peripheral blood or finding of \geq 5% blasts in the bone marrow not attributable to another cause. The appearance of new dysplastic changes should also be considered relapse. The reappearance or development of cytologically proven extramedullary disease also indicates relapse. Molecular and/or genetic relapse is characterized by reappearance of a cytogenetic or molecular abnormality.

